8 GENERAL DESIGN ISSUES

The study design consists of three parallel arms: placebo and two final doses of SRX246 (120 mg BID and 160 mg BID). Thirty-six patients will be randomized into each study arm. Since we have only given SRX246 to generally healthy subjects thus far, and since some HD patients may be frailer population, we have elected to initiate treatment at 80 mg BID; to increase the dose of drug to 120 mg BID after two weeks in those patients who have tolerated the starting dose; and to increase the dose of drug again after 2 additional weeks in those patients who are taking 160 mg BID. Subjects in the placebo group will take capsules that will be identical in appearance to those containing SRX246. Thus, patients and study staff will both be blind to treatment, and twice as many Subjects will receive active agent as placebo. The placebo group will be used for comparison with each active drug group.

Subjects who are unable to increase their dose of drug can remain in the study at the highest dose they can tolerate, and Subjects who find the drug intolerable can reduce the dose of drug (to 80 mg BID of SRX246 or placebo, but no lower without dropping out of the study). The goal is to study the behavioral scales in as many people as possible because we feel that this will be important to the clinical research community.

At the end of the trial, data from all Subjects who were given placebo will be combined, and two pairwise tests will be performed (120 mg vs placebo, 160 mg vs placebo--see below).

It may be necessary to screen as many as 150 candidates to enroll 108 Subjects. Up to 20 NeuroNEXT sites may participate in the study, with each site's goal to enroll about 5-6 Subjects within the first 18 months of the trial.

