The results of the power analysis are shown in Figure 4 below. The Figure shows the single-arm sample size (n_P) as a function of the P group proportion (π_P), and the group proportion difference ($\pi_P - \pi_T$) paneled by α -level. As discussed, the combination of $\pi_P - \pi_T = 0.20$ and $\pi_P = 0.80$ appear to be reasonable bounds for sample size selection. In the left-hand panel, the upper red line shows that conducting two tests each at $\alpha = .025$ and 80% power requires approximately 35 participants per group for the smallest proposed control proportion ($\pi_P = 0.80$) and the largest proportion difference ($\pi_P - \pi_T = 0.20$). Therefore, we propose a total sample size of $N = 3n_P = 105$.

[figure not shown]
Figure 4. Sample size for the placebo group as a function of effect size, placebo proportion, and alpha-level (80% power).

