Further Sample Size Considerations. The power analysis suggests that a total sample size of $2n_p = 70$ will be used for each comparison of completer proportions (120mg vs placebo, 160mg vs placebo). The margin used to derive this sample size, $\delta = 0.50$, allows the possibility of a relatively small proportion of completers in the T group. For example, if $\pi_p = 0.90$, H_0 will be rejected if $\pi_p > 0.40$, meaning there could be a minority of completers. In order to assess the sensitivity of the sample size to a change in margin value, we examined the power of the z-test for the observed values in Table 4 with $n_p = n_T = 35$ fixed for all calculations, and $\alpha = 0.025$ to allow for two comparisons. Figure 5 shows power as a function of the Table 4 P group proportions, group proportion differences, and various margin values. The vertical dashed line indicates the mean group difference of 0.08 (mean P proportion is 0.91), and 80% power is indicated by a horizontal dashed line. Using the mean Table 4 values as a reference, the middle panel indicates that with the selected sample size the margin can be decreased to 0.30 and still provide 80% power to reject H_0 (the point defined by the intersection of the dashed lines). Assuming the mean values of Table 4, the 0.30 margin allows for rejection of H_0 for $\pi_T > 0.61$. If the proportions of the proposed study are equal to the mean values of Table 4, then the statistical power will be high enough to reject H_0 for a margin as low as 0.30 with a majority of completers in the T group. We also note that the left-most panel of Figure 5 shows that an even lower margin (e.g., $\delta = 0.20$) will provide adequate power if the P and T proportions are relatively close to 1 and approximately equal (close to no difference).

Figure 5. Power for $n = 35$ per group as a function of Table 4 placebo group proportion, group proportion difference (placebo minus treatment), and margin value.

The dashed horizontal line indicates the conventional 80% power value and the vertical dashed line indicates the average Table 4 group difference.

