$$H_0: \pi_{\text{placebo}} - \pi_{120\text{mg}} \geq \delta$$

vs.

$$H_A: \pi_{\text{placebo}} - \pi_{120\text{mg}} < \delta.$$

For the purposes of this study, the non-inferiority margin was set to $\delta = 0.5$, which is the same value used in a series of clinical trials sponsored by the Huntington Study Group ([HSG, 1998](#); [HSG, 2003](#); [HSG, 2004](#); [HSG/TETRA-HD Investigators, 2009](#)). Using this threshold means that when H_0 is rejected, $\pi_{120\text{mg}} - \pi_{\text{placebo}} < 0.5$. Or, equivalently, the tolerability in the treated group is less than 50% lower than the tolerability in the placebo group, which is taken to be a negligible (non-meaningful) difference in tolerability. Thus, non-inferiority of tolerability within the margin is consistent with the rejection of the null hypothesis and will constitute a Go decision for further consideration of that dose of SRX246, perhaps in a phase IIb study to detect signs of activity. Conversely, failure to reject the null hypothesis would imply that there could be tolerability concerns and will result in a No-Go decision for that dose. Note that rejection of H_0 does not necessarily mean there is strict equivalence among the groups (i.e., does not imply that the difference is 0). Rather, any tolerability difference is below the acceptable 50% threshold.

The statistical test of H_0 will be performed using a one-sided CI for the difference of the proportions based on exact methods. Exact methods have known sampling distributions in contrast to asymptotic methods that have approximate sampling distributions ([Agresti, 2003](#)). Exact methods are preferable because their confidence intervals (CIs) have a minimum coverage probability, especially for small sample sizes (the minimum is $1 - \alpha$). The CI to be used corresponds to inverting a family of exact tests, with the 97.5% CI ($\alpha = 0.025$) including all the values that are not rejected at the .025 level in the corresponding test. Though an exact CI has a minimum coverage probability of $1 - \alpha$, its length can be too long, which means the associated inverted test has low statistical power. To address this issue, and to ensure that H_0 is evaluated using the highest possible statistical power, a computer-intensive method will be used to select the shortest one-sided CI for testing ([Wang, 2010](#)).

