The exact testing assumes binomial distributions for the variables. A study participant is classified as meeting the definition for tolerability if they complete the study on assigned treatment, or as a non-completer if they do not finish the trial (withdrawal for any reason) or have to withdraw from assigned treatment before the end of the study. The number of participants meeting this definition in the placebo group and each treatment group (e.g., 120 mg) is binomially distributed. There is an analytic formula for the joint probability function, which forms the basis of the exact test.

Suppose that $\theta = \pi_{\text{placebo}} - \pi_{120\text{mg}}$, so that $H_0: \theta \geq 0.5$ and $H_A: \theta < 0.5$. We reject H_0 if the one-tailed $1 - \alpha$ CI for θ does not contain 0.5. When the proportions are equal, $\theta = 0$, and when tolerability is higher in the placebo group, $\theta > 0$. Therefore, we are interested in the lower one-sided CI with range $[-1, \text{UCI}]$, where UCI is the upper CI limit. If $\text{UCI} < 0.5$, then we reject H_0 . If $\text{UCI} \geq 0.5$, then we do not reject H_0 . In summary,

$$\text{UCI} < 0.5, \quad \text{Reject } H_0;$$

$$\text{UCI} \geq 0.5, \quad \text{Do Not Reject } H_0.$$

For each analysis, we set $\alpha = 0.025$, which means H_0 is tested with a one-sided $1 - \alpha = 0.975$ CI.

An additional consideration is that using the usual asymptotic test can be inaccurate with smaller sample sizes, especially when π_{placebo} (or $\pi_{120\text{mg}}$) are close to 1.0, as is anticipated in this study ([Fagerland, 2011](#)). Computer intensive exact methods can have better performance under these conditions ([Santner, 2007](#)). The shortest lower one-sided CI will be computed with a computer-intensive ranking-based method ([Wang, 2010](#)). Wang's method appears to have superior performance to other approaches, and software is readily available ([Wang, 2012](#)).

The method will be computed with the `BinomCI()` function of the `ExactCI` package ([Shan & Wang, 2013](#)) for the R computing software.

The results of the tolerability analysis will be summarized graphically, with a bar plot showing the proportion difference and one-sided CI for each group comparison. The results will also be depicted as in [Table 2](#) below.

Table 2. Proportion of Participants Meeting Study Definition for Tolerability

Group	Placebo (N = XX)	120 mg (N = XX)	160 mg (N = XX)
Number (%)	XX (XX%)	XX (XX%)	XX (XX%)

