9. SAMPLE SIZE JUSTIFICATION

Required sample size was estimated for the primary objective of evaluating the tolerability of SRX246. As previously discussed, this objective will be met by conducting a non-inferiority test of the proportion of completers among the placebo group and each of the treatment groups (separate tests for placebo vs. 120 mg and placebo vs. 160 mg). As described in [section 7](#), the non-inferiority test for the primary objective will be based on exact methods with a computer-intensive ranking procedure to ensure the highest statistical power ([Wang, 2010](#)). It is impractical to use the aforementioned procedure to estimate the required sample size. Therefore, an approximation was used based on the asymptotic test of the difference between two proportions.

Let us again denote the proportion of participants meeting the study definition for tolerability in the placebo group as $\pi_{placebo}$, and the proportion in the 120 mg group as π_{120mg} . The sample size for achieving 80% power for the placebo vs 120 mg groups can be calculated with the following equation,

$$n_{placebo} = \frac{(Z_{.025/2} + Z_{.80/2})^2 \cdot [\pi_{placebo} \cdot (1 - \pi_{placebo}) + \pi_{120mg} \cdot (1 - \pi_{120mg})]}{(\delta - \pi_{placebo} - \pi_{120mg})^2},$$

where δ is the threshold previously discussed, $n_{placebo}$ is the sample size for the placebo group, and the total for the entire study is $N = 3 \cdot n_{placebo}$.

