The above equation indicates that a power analysis for this scenario requires estimates for the values of $\pi_{placebo}$, π_{120mg} , and δ . A power analysis was conducted using estimated values of the parameters obtained from previous research. Following the practice of the Huntington Study Group ([HSG, 1998](#); [HSG, 2003](#); [HSG, 2004](#); [HSG/TETRA-HD Investigators, 2009](#)), the margin was set at $\delta = 0.50$ for all analysis. A difference of <50% between groups is considered acceptable because of the paucity of effective treatments for HD ([HSG, 1998](#)). For the remaining parameters, plausible values were based on published literature for relevant randomized clinical trials (RCTs) in HD ([HSG, 1998](#); [HSG, 2003](#); [HSG, 2004](#); [HSG/TETRA-HD Investigators, 2009](#); [Kieburtz et al, 2010](#); [Squitieri et al, 2013](#)). [Table 4](#) below shows completer information for placebo and treatment groups of six HD RCTs employing various drugs (for studies with multiple treatment groups, group with the smallest percentage of completers is shown). Placebo completion rates across the six studies ranged from 82%-97%, and the observed treatment group differences ranged from 0%-18%.

In light of the information in Table 4, sample size was computed for:

- $\pi_{placebo} = 0.80, 0.85, 0.90, 0.95$, and
- $\pi_{placebo} - \pi_{treatment} = 0.01, 0.02, \dots, 0.19, 0.20$.

[figure not shown]
It should be noted that the minimum $\pi_{placebo} = 0.80$ is less than any placebo value in Table 4, and the maximum difference ($\pi_{placebo} - \pi_{120mg}$) of .20 is greater than any observed difference in Table 4. Therefore, these values constitute reasonable bounds for assessing required sample size for this study. The non-inferiority test is single-tailed, and type I error rates of $\alpha = 0.05/2 = 0.025$ and $\alpha = 0.10/2 = 0.05$ were used to allow for two comparisons (each dose level versus placebo), with target power set at 80%.

Table 4. Tolerability Statistics from HD Clinical Trials.

Study	Drug	N	Placebo	Treatment	Difference
HSG (1998)	OPC-14117	64	94%	81%	13%
HSG (2003)	Riluzole	63	91%	87%	4%
HSG (2004)	Minocycline	60	96%	78%	18%
HSG/TETRA-HD (2009)	Tetrabenazine	84	97%	91%	+6%
Kieburtz et al (2010)	Latrepirdine	91	82%	87%	-5%
Squitieri et al (2013)	Pridopidine	353	86%	86%	0%

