The results of the power analysis are shown in [Figure 2](#) below. The figure shows the single-arm sample size ($n_{placebo}$) as a function of $\pi_{placebo}$ and the group proportion difference ($\pi_{placebo} - \pi_{120mg}$), paneled by α -level. In the left-hand panel, the upper red line shows that conducting two tests each at $\alpha = 0.025$ and 80% power requires approximately 36 participants per group for the smallest proposed control proportion ($\pi_{placebo} = 0.80$) and the largest proportion difference ($\pi_{placebo} - \pi_{treatment} = 0.20$). Therefore, we proposed a total sample size of $N = 3 \times 36 = 108$. The power analysis suggests that a total sample size of $2 \times 36 = 72$ will be used for each group comparison of completer proportions (120 mg vs placebo, 160 mg vs placebo). The margin used to derive this sample size ($\delta = 0.5$) allows the possibility of a relatively small proportion of completers in the treatment group. For example, if $\pi_{placebo} = 0.90$, H_0 will be rejected if $\pi_{placebo} > 0.04$, meaning there could be a minority of completers.

Figure 2. Sample Size for the Placebo Group as a Function of Effect Size, Placebo Proportion, and Alpha-Level (80% Power)

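### Do the misprinted equation and worked boundary in SAP Section 9 put the 36 per arm in doubt?

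*SAP*

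**What the plan says.** SAP Section 9 sizes the trial for two one-sided non-inferiority tests, each at 0.025, with 80% power and a margin of 0.50. It uses an asymptotic formula because sizing with the planned exact method was judged impractical. The Z terms carry the subscripts .025/2 and .80/2, and the denominator ends "\delta - \pi_{placebo} - \pi_{120mg})^2". From a figure it then reads about 36 per group for placebo 0.80 and a difference of 0.20, hence 108 in total and 72 per comparison.

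To show how permissive the margin is, Section 9 takes placebo completion as 0.90 and says "H_0 will be rejected if $\pi_{placebo} > 0.04$, meaning there could be a minority of completers". Protocol Section 8.2 has the same example as "H_0 will be rejected if $\pi_p > 0.40$, meaning there could be a minority of completers". For the same worst case Protocol 8.2 arrives at about 35 per group, 70 per comparison and 105 in total, while Protocol Section 8 says "Thirty-six patients will be randomized into each study arm" and Protocol 2.1.1 plans 108.

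SAP Section 7 displays the null hypothesis as placebo minus 120 mg at or above the margin, and the alternative as below it. Its decision rule is "If $\text{UCI} < 0.5$, then we reject H_0". Between the two, a sentence interpreting the result says that "when H_0 is rejected, $\pi_{120\text{mg}} - \pi_{\text{placebo}} < 0.5".

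**The concern.** A sample-size equation is printed so that a reader can check the number, and this one fails the check. Section 9 says "The non-inferiority test is single-tailed, and type I error rates of $\alpha = 0.05/2 = 0.025", so 0.025 is already the per-comparison level of a one-sided test, yet the equation halves it again. The term Z with subscript .80/2 matches no usual quantile for 80% power. The printed denominator subtracts both proportions from the margin instead of subtracting their difference.

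The worked example bounds the placebo proportion in the sentence that has just fixed it, and its value is a tenth of what it should be. The interpretive inequality in Section 7 runs the wrong way: read literally, it would be satisfied however far tolerability on SRX246 fell below placebo. The two documents also differ by one participant per arm.

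If these were more than slips, either the trial could be mis-sized for its primary endpoint or the Go/No-Go criterion could be applied in the wrong direction.

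**Working it through.** **Inputs** (SAP Section 9; the same values are in Protocol 8.2): one-sided alpha 0.025 per comparison; power 80%; margin 0.50; placebo 0.80; difference 0.20, so treatment 0.60; equal arms. There is no inflation for dropout, because non-completion is itself the endpoint. The variance term is 0.80 × 0.20 + 0.60 × 0.40 = 0.16 + 0.24 = 0.40.

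**The plan's own figure.** The standard unpooled formula is n = (z_0.975 + z_0.80)² × [πP(1 − πP) + πT(1 − πT)] / (δ − (πP − πT))².

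- (1.960 + 0.842)² = 7.849
- 7.849 × 0.40 / (0.50 − 0.20)² = 7.849 × 0.40 / 0.09 = 34.88, so 35 per arm and 3 × 35 = 105. This is the Protocol 8.2 figure.
- Approximate power is Φ(0.30 / √(0.40/n) − 1.960): 0.801 at n = 35 and 0.812 at n = 36.

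So 36 per arm (3 × 36 = 108) slightly exceeds the requirement. At the same difference of 0.20, the formula needs 31, 27 and 21 per arm for placebo 0.85, 0.90 and 0.95, so 0.80 is the demanding case, as both documents say.

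**The equation as printed**, under different readings:

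| Z terms | Denominator | n | Per arm |
|---|---|---|---|
| As printed: (2.2414 + 0.2533)² = 6.224 | As printed: (0.5 − 0.8 − 0.6)² = 0.81 | 3.07 | 4 |
| Standard: 7.849 | As printed: 0.81 | 3.88 | 4 |
| As printed: 6.224 | Brackets restored: 0.09 | 27.66 | 28 |
| Alpha halved again, z_0.80 for power | Brackets restored: 0.09 | 42.24 | 43 |
| Alpha halved again, .80/2 read as .20/2 | Brackets restored: 0.09 | 55.16 | 56 |
| Standard: 7.849 | Brackets restored: 0.09 | 34.88 | 35 |

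Only the last row comes near 36. The documents' 35 and 36 therefore fit a calculation with the correct formula, and the printed equation is a faulty transcription of it. The 28 per arm in the third row would have had approximate power of 0.709, so the trial was evidently not sized that way.

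**The worked boundary.** The alternative holds when πP − πT < 0.50. With πP = 0.90 this means πT > 0.90 − 0.50 = 0.40. The Protocol has the right value with a placebo subscript; the SAP has that subscript and 0.04. The sentence before it in the SAP says the point concerns completers in the treatment group. The same Protocol paragraph puts the boundary for the 0.30 margin on the treatment arm, at 0.61.

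**The inequality in Section 7.** The displayed alternative is placebo minus 120 mg below 0.50. The sentence after the reversed inequality describes treatment tolerability as less than 50% below placebo, which is the right direction. The decision rule defines θ as placebo minus 120 mg and compares the upper limit for θ with 0.5. Three of the four statements agree, and the rule that analysts will program is one of the three.

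**The case for a change.** The case for correcting the text is reasonable. The SAP says its analyses support the final study report and will go into regulatory submissions or manuscripts. A reader who applies the printed equation gets 4 or 28 and might challenge a sound sample size. The example is the SAP's only numerical illustration of what a 50-point margin allows, and 4% completers is a very different picture from 40%. Several slips cluster around the primary endpoint, and the repair is a few words. The Z subscripts cannot be put down to text conversion, because no literal reading of them gives 35 or 36 even with the brackets restored.

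All of this stands as a description of the text. Two points limit it. The figure of 4 depends on brackets that may simply have been lost in conversion; with them restored the equation gives 28. The sample size also remains checkable without the equation: Protocol 8.2 prints the test statistic with the correct numerator, and both documents list every input. The gap between the Protocol's "we propose a total sample size of $N = 3n_P = 105" and 108 is one participant per arm. Both derivations are worded as approximate, and the Protocol's own design section already fixes 36.

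**Conclusion.** The slips are real but clerical, and no change to the plan follows. The stated inputs require 35 per arm; the plan has 36, with asymptotic power of 81.2% against a target of 80%. The hypotheses, the 0.50 margin, the 0.025 level and the rule on the upper confidence limit are correct and do not draw on the Section 9 equation. Correcting the subscripts, the brackets, 0.04 to 0.40 with the arm label, and the reversed inequality would leave the sample size, the analysis and every Go/No-Go decision as they are. An analyst working from the displayed hypotheses and the decision rule would not be misled.

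This rests on the asymptotic approximation that the SAP itself uses for sizing. Enumerating the binomial outcomes for the asymptotic test gives power of 0.825 at 36 per arm. The power of the planned exact interval was not computed. It also takes the worst case of 0.80 and 0.60 as given, and does not address whether 0.50 is a sensible margin.

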10. SAFETY MONITORING

10.1. Independent Medical Monitor

The PPI will appoint a Medical Safety Monitor (MSM). The MSM responsibilities will include independent review of safety data, including but not limited to review of all events that meet the regulatory definition of an SAEs in real-time upon notification via the NeuroNEXT Online Adverse Event Reporting System (AERS). In addition to performing real-time reviews of all SAEs (as described in [section 4](#)), the MSM will also receive aggregate, blinded reports of all AEs for review on a quarterly basis (or as requested). These aggregate reports will summarize all AEs by severity, attribution (expected or unexpected), and relationship to study drug procedures in a tabular form. The MSM will be responsible for providing a written summary of this review to the DCC. Should any concerns arise due to observed trends, the MSM will send a written recommendation to the DCC requesting that the report be forwarded to the Protocol PIs and/or the Data and Safety Monitoring Board (DSMB), as appropriate.

10.2. Data and Safety Monitoring Board

The monitoring of study participant safety and data quality will follow the NINDS Guidelines for Data and Safety Monitoring in Clinical Trials. A DSMB, appointed by NIH/NINDS, will meet at approximately six-month intervals (or as determined by the NINDS) to review partially unblinded study data provided by the study statistician. The DSMB will periodically review and evaluate the accumulated data for participant safety, adverse events, study conduct, and study progress. The DSMB may suggest changes to the protocol or consent form to the PPI as a consequence of AEs. The DSMB may also make recommendations to NINDS concerning continuation, modification, or termination of the study. The frequency and format of DSMB meetings and reports will be agreed upon prior to study enrollment.

REFERENCES

Agresti A (2003). "Dealing with discreteness: Making 'exact' confidence intervals for proportions, differences of proportions, and odds ratios more exact," *Statistical Methods in Medical Research*, 12:3-21.

Blackwelder WC (1982). "Proving the Null Hypothesis" in clinical trials," *Controlled Clinical Trials*, 3: 345-353.

Detry MA and Lewis RJ (2014). "The intention-to-treat principle: How to assess the true effect of choosing a medical treatment," *Journal of the American Medical Association*, 312: 85-86.

Huntington Study Group (1998). "Safety and tolerability of the free-radical scavenger OPC-14117 in Huntington's disease," *Neurology*, 50:1366-1373.

Huntington Study Group (2003). "Dosage effects of riluzole in Huntington's disease: A multicenter placebocontrolled study," *Neurology*, 61:1551-1556.

Huntington Study Group (2004). "Minocycline safety and tolerability in Huntington disease," *Neurology*, 63:547549.

Huntington Study Group/TETRA-HD Investigators (2009). "Tetrabenazine as antichorea therapy in Huntington disease: An open-label continuation study," *BMC Neurology*, 9: 62. Erratum in: *BMC Neurology*, 11: 18.

